10.2.2.2 Analysis of Secondary and Other Efficacy Endpoints

The detail of analysis method for secondary and other efficacy endpoints will be described in the SAP. The detail model for each endpoint will be described in the SAP.

The following secondary and other efficacy endpoints will be analyzed using the MMRM similar to the analyses for the primary endpoint.

- Change from baseline in average daily duration (**minutes**) of sunlight exposure between 1 hour post sunrise and 1 hour pre-sunset without prodromal symptoms.
- Change from baseline in average daily mean duration (**minutes**) of sunlight exposure between 1 hour post sunrise and 1 hour pre-sunset without prodromal symptoms. The daily mean duration is considered as multiple periods of sunlight exposure in each day and measurable by sum of duration of each period divided by number of periods.
- Change from baseline in average daily duration (**minutes**) of prodromal symptoms during 16-week double-blind treatment period.
- Change from baseline in average daily duration (**minutes**) of pain events during 16-week double-blind treatment period.
- The average daily mean intensity of the subject's prodromal symptoms during 16-week double-blind treatment period.
- The average daily mean intensity of the subject's pain events during 16-week double-blind treatment period.
- Change from baseline for all total score and total score in each domain of physical function, anxiety, depression, fatigue, sleep disturbance, ability to participate in social roles and activities, pain interference, pain intensity in PROMIS-57.
- PGIC.

The following endpoints will be analyzed; a negative binomial regression model with log link will be fitted. The model will include treatment as fixed effect, and baseline total number of sunlight exposure episodes with prodromal symptoms as the covariate. The estimated incidence rate (IR) and its 95% confidence interval for each treatment group, incidence rate ratio (IRR) of each active MT-7117 treatment group versus placebo, 95% confidence interval of the IRR together with relevant p-values will be reported.

- Total number of sunlight exposure episodes with prodromal symptoms during 16-week double-blind treatment period.
- Total number of pain events during 16-week double-blind treatment period.

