- e Vital signs include measurement of sitting blood pressure, pulse rate, and body temperature.
- f At Visits 3 and 4, subjects will have mobile units measure liver function markers (ALT, AST, GGT, ALP, direct and total bilirubin). Blood samples for liver function markers will be shipped to the central laboratory.
- g Plasma total porphyrins and erythrocyte protoporphyrin will be assessed at Visits 1, 6 and 8. Results reports will be sent to the site for data collection.
- h For female subjects of child-bearing potential, a serum pregnancy test will be performed at Visit 1 and a urine pregnancy test will be performed at Visits 2 and Visits 5 through 9.

- i PK blood samples for MT-7117 will be collected and processed at Visit 2 (pre-dose), Visits 5 through 7 (any time), and Visit 8 (at the visit and 3 to 4 hours after the first PK sample collection [both post-dose]). Date and time of most recent dose, and date and time of PK sample collection will be recorded.
- j Subjects will be asked whether they receive active or placebo treatment at Visit 8.
- k Sunlight exposure data, presence of prodromal symptoms and pain, their severity, and their onset/duration will be collected from Visits 1 through 9. Diary training will be performed at the first in-clinic visit during the screening period.
- l In-clinic sunlight exposure test should be done once before randomization and once at Visit 8.
- m Nevi evaluation will be performed locally by a dermatologist or qualified site staff. Baseline nevi evaluation will be performed at any time during the Screening period before Randomization. The Nevi evaluation at Visit 9 is to assess for the reversibility if any suspicious nevi changes were observed during treatment as per the investigator's (and/or dermatologist's or other qualified site staff) judgment. Any follow-up will be recorded in the eCRF.
- n These assessments will be performed at Week 16 or early termination.
- o All subjects will return to the study site for a follow-up visit at 6 weeks after end of treatment visit (Week 16 or early termination).
- p The exit interview can be assessed at Visit 9 or as a post study follow-up phone call or online survey.

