### 2.2 Secondary Efficacy Endpoints

- Change from baseline in average daily duration (minutes) of sunlight exposure between 1 hour post sunrise and 1 hour pre-sunset without prodromal symptoms at Week 16.
- Change from baseline in average daily mean duration (minutes) of sunlight exposure between 1 hour post sunrise and 1 hour pre-sunset without prodromal symptoms. The daily mean duration is considered as multiple periods of sunlight exposure in each day and measurable by sum of duration of each period divided by number of periods.
- Total number of sunlight exposure episodes with prodromal symptoms during 16-week double-blind treatment period.
- The average daily mean intensity of the subject's prodromal symptoms during 16-week double-blind treatment period.
- Change from baseline in average daily duration (minutes) of prodromal symptoms during 16-week double-blind treatment period.
- The change from baseline and % change from baseline in melanin density at Week 8, 16, and 22 by skin segments. Average of 6 skin segments for the change from Baseline and % change from baseline in melanin density at Week 8, 16, and 22.
- Total number of pain events during 16-week double-blind treatment period.

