### 2.3 Other Efficacy Endpoints

- Change from baseline for in-clinic sunlight exposure time (minutes) to the first prodromal symptoms.
- Total time (hours) during 16-week double-blind treatment period in duration of sunlight exposure between 1 hour post sunrise and 1 hour pre-sunset without prodromal symptoms.

- Total number of days subject is exposed to sunlight for any duration between 1 hour post sunrise and 1 hour pre-sunset without prodromal symptoms during 16-week double-blind treatment period.
- Change from baseline in average daily duration (minutes) of sunlight exposure between 1 hour post sunrise and 1 hour pre-sunset on Saturday without prodromal symptoms at Week 16.
- Change from baseline in average daily duration of sunlight exposure regardless of time of day without prodromal symptoms assessed at Week 16.
- The average daily mean intensity of the subject's pain events during 16-week double-blind treatment period.
- Change from baseline in average daily duration (minutes) of pain events during 16-week double-blind treatment period.
- Change from baseline for all total score and total score in each domain of physical function, anxiety, depression, fatigue, sleep disturbance, ability to participate in social roles and activities, pain interference, pain intensity in PROMIS 57.
- Patient Global Impression of Change (PGIC).

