#### **2.6 Demographic and Other**

##### **2.6.1 Demographic and Baseline Characteristic**

The following subject demographic and baseline characteristic are collected.

- Age (years)
- Sex
- Race
- Ethnicity
- Weight (kg)
- Height (cm)
- BMI (kg/m^2)
- Baseline average sunlight exposure duration without prodromal symptoms
- Baseline average daily duration of pain
- Seasonality (Randomized between Mar 1 and Aug 31 inclusive, other)

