### 7.11.2 Analysis of Secondary and Other Efficacy Endpoints

The following continuous secondary and other efficacy endpoints will be analyzed using MMRM similar to the analyses for the primary endpoint.

- Change from baseline in average daily duration (minutes) of sunlight exposure between 1 hour post sunrise and 1 hour pre-sunset without prodromal symptoms.
  - The model will include fixed categorical terms for treatment, randomization strata, visit, and treatment by visit interaction together with continuous covariate terms for baseline value and baseline value by visit interaction.
  - The figure of LS mean with standard error will be plotted.
- Change from baseline in average daily mean duration (minutes) of sunlight exposure between 1 hour post sunrise and 1 hour pre-sunset without prodromal symptoms. The daily mean duration is considered as multiple periods of sunlight exposure in each day and measurable by sum of duration of each period divided by number of periods.
  - The model will include fixed categorical terms for treatment, randomization strata, visit, and treatment by visit interaction together with continuous covariate terms for baseline value and baseline value by visit interaction.
  - The figure of LS mean with standard error will be plotted.
- Change from baseline in average daily duration (minutes) of prodromal symptoms during 16-week double-blind treatment period.
  - The model will include fixed categorical terms for treatment, randomization strata, visit, and treatment by visit interaction together with continuous covariate terms for baseline value and baseline value by visit interaction.
  - The figure of LS mean with standard error will be plotted.
- Change from baseline in average daily duration (minutes) of pain events during 16-week double-blind treatment period.
  - The model will include fixed categorical terms for treatment, randomization strata, visit, and treatment by visit interaction together with continuous covariate terms for baseline value and baseline value by visit interaction.

- The figure of LS mean with standard error will be plotted.
- Change from baseline in average daily mean intensity of the patient's prodromal symptoms during 16 week double-blind treatment period.
  - The model will include fixed categorical terms for treatment, randomization strata, visit, and treatment by visit interaction together with continuous covariate terms for baseline value and baseline value by visit interaction.

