The following endpoints will be analyzed using a negative binomial regression model with log link will be fitted. The model will include treatment and the baseline average daily sunlight exposure time without prodromal symptoms ( $\leq 30$  min or  $> 30$  min) as fixed effect, and baseline total number of sunlight exposure episodes with prodromal symptoms as the covariate. The estimated incidence rate (IR) and its 95% confidence interval for each treatment group, incidence rate ratio (IRR) of each active MT-7117 treatment group versus placebo, 95% confidence interval of the IRR together with relevant p-values will be reported.

- Total number of sunlight exposure episodes with prodromal symptoms during 16-week double-blind treatment period.
- Total number of pain events during 16-week double-blind treatment period.

The following example SAS code will be used;

```
[REDACTED SAS CODE]
```

The following endpoints will be summarized using descriptive statistics and Wilcoxon's rank sum test.

- Total number of days subject is exposed to sunlight for any duration between 1 hour post sunrise and 1 hour pre-sunset without prodromal symptoms during 16-week double-blind treatment period.

The following endpoint will be analyzed using ANCOVA or ANOVA model.

- Change from baseline for In-clinic sunlight exposure time (minutes) to the first prodromal symptoms.
  - The model will include fixed categorical terms for treatment, randomization strata, together with continuous covariate terms for baseline value.
- Change from baseline in Average daily duration (minutes) of sunlight exposure between 1 hour post sunrise and 1 hour pre-sunset on Saturday without prodromal symptoms at Week 16. The average value is calculated for Saturdays within the windows defined in section 5.4.
  - The model will include fixed categorical terms for treatment, randomization strata, together with continuous covariate terms for baseline value.
- Change from baseline in average daily duration of sunlight exposure regardless of time of day without prodromal symptoms assessed at Week 16
  - The model will include fixed categorical terms for treatment, randomization strata, together with continuous covariate terms for baseline value.

- Total time (hours) during 16-week double-blind treatment period in duration of sunlight exposure between 1 hour post sunrise and 1 hour pre-sunset without prodromal symptoms.

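### The pain-event count and total symptom-free hours are modelled without their own continuous baseline: a possible loss of precision from nil to moderate, and no bias

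*SAP*

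**What the plan says.** **Count endpoints.** SAP 7.11.2 specifies one negative binomial model with log link for two 16-week totals: exposure episodes with prodromal symptoms, and pain events. The terms are treatment, the ≤30/>30 min baseline factor, and "baseline total number of sunlight exposure episodes with prodromal symptoms as the covariate". Protocol 10.2.2.2 names the same covariate for both counts, without the stratum: "The model will include treatment as fixed effect, and baseline total number of sunlight exposure episodes with prodromal symptoms as the covariate". It also delegates model detail: "The detail model for each endpoint will be described in the SAP". The pain count is a listed secondary endpoint (SAP 2.2): "Total number of pain events during 16-week double-blind treatment period".

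**Total hours.** SAP 2.3 lists as an other endpoint "Total time (hours) during 16-week double-blind treatment period in duration of sunlight exposure" without prodromal symptoms. SAP 7.11.2 puts it under ANCOVA or ANOVA, with treatment and randomization strata as the only terms. The other three endpoints in that list also carry a continuous baseline value.

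**Baseline data.** SAP Table 1, footnote k: "Sunlight exposure data, presence of prodromal symptoms and pain, their severity, and their onset/duration will be collected from Visits 1 through 9". SAP Table 4 sets the baseline window at Day -14 to -1, and Table 1, footnote a, requires at least 7 days of exposure data before randomization. SAP 2.6.1 already lists "Baseline average sunlight exposure duration without prodromal symptoms" and a baseline pain duration among the baseline characteristics.

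**The concern.** The prodromal-episode count is a 16-week total, not a change score, and the SAP adjusts it for its own baseline. The pain count is the same kind of endpoint under the same model, yet it receives the prodromal baseline and no pain baseline. The pain-duration model ("Change from baseline in average daily duration (minutes) of pain events during 16-week double-blind treatment period") and the pain-intensity model do use their own baselines. Those are change-from-baseline analyses, where the baseline enters naturally. They show that baseline pain data exist, not that the count model is wrong.

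For total hours, the only baseline information used is the symptom-free exposure time cut at 30 minutes, so the variation within each stratum is discarded.

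What is at stake is precision. With about 34 subjects per arm in a rare disease, a prognostic baseline that has already been collected is worth using if it carries information.

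**Working it through.** **Inputs from the documents.** 34 per arm, 102 in total, 1:1:1; two-sided 5%; baseline of 7 to 14 diary days; 112 treatment days. The sample size does not rest on a calculation (SAP 6), so there is no stated power or SD to reproduce. Every correlation, rate and variance below is an assumption.

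**Total hours, closed form.** Let r be the correlation of the continuous baseline with the 16-week total, and p the proportion above 30 minutes. For a normal baseline, the two-level stratum captures R²s = φ(c)² / [p(1-p)] of its variance, where c is the normal cut-point with proportion p above it. At p = 0.5, R²s = 0.1592/0.25 = 2/π = 0.637. The ratio of standard errors, with versus without the continuous baseline, is sqrt[(1 - r²)/(1 - r²·R²s)].

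- r = 0.3: sqrt(0.910/0.943) = 0.983, or -1.7%
- r = 0.5: sqrt(0.750/0.841) = 0.944, or -5.6%
- r = 0.7: sqrt(0.510/0.688) = 0.861, or -13.9%

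With p = 0.2 or 0.8, R²s = 0.490 and the ratios are 0.976, 0.924 and 0.819.

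**Total hours, simulation.** 4000 trials of 102 subjects per setting, with 50%, 30% or 20% in the upper stratum:

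| r | Change in SE |
|---|---|
| 0 | +0.5% |
| 0.1 | +0.2% to +0.3% |
| 0.3 | -1.3% to -1.9% |
| 0.5 | -5.1% to -7.1% |
| 0.7 | -13.5% to -17.7% |

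For scale, 34 per arm gives power 0.801 for a 0.68 SD difference with no adjustment. At p = 0.5, power with the stratum only versus with the baseline added is 0.864 versus 0.899 at r = 0.5, and 0.922 versus 0.975 at r = 0.7.

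**Pain count, simulation.** Three arms of 34 with no treatment effect. Pain and prodromal propensities are lognormal with the same log-SD, correlated 0.2 to 0.8. There are 40 prodromal episodes and 2, 5 or 12 pain events per 112 days, a baseline of 7 to 14 days, and period-specific gamma noise with variance 0.25. There were 400 to 900 trials per setting. The SAP model is compared with the same model plus the raw baseline pain rate per diary day.

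| Between-subject log-SD | Change in mean model SE of log rate ratio | Change in empirical SD of the estimate |
|---|---|---|
| 0.3 | 0.0% to -0.7% | +1.0% to -0.2% |
| 0.5 | -0.3% to -3.2% | +1.0% to -5.3% |
| 0.7 | -0.7% to -7.0% | +1.7% to -11.1% |
| 1.0 | -2.1% to -12.4% | -1.7% to -23.7% |

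At log-SD 0 the model SE changes by 0.0% to +0.1%. Where the covariate carries no information, the empirical SD rises by 0.1% to 1.4%. The share of subjects with no baseline pain event is 83–86% at 2 events per 16 weeks, 65–71% at 5, and 38–52% at 12.

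The absolute model SEs are too small when heterogeneity is high. At log-SD 1.0, correlation 0.2 and 12 events, the mean model SE is 0.266 against an empirical SD of 0.360, with type I error 0.163. Only the with/without comparison should be read from this table.

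**Pain count, second simulation with a different design.** 34 versus 34, true rate ratio 0.6, log-SD 0.8, baseline counts entered as log(1 + count), 400 replicates. With latent rates correlated 0.5, the variance ratio is 0.887, 0.768 and 0.637 at 0.3, 1 and 3 baseline pain events per 14 days, a fall of 11% to 36%. With uncorrelated rates and 3 events it is 0.506. With no between-subject differences it is 1.013. The mean estimated rate ratio is 0.59 to 0.61 under both models in every setting, and 1.01 versus 1.00 under the null, so no bias is visible from the omission.

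**Scale of the covariate.** A smaller check of five settings with 200 trials each gave almost the same gain for a raw and a log-scaled rate. It ran from nil at log-SD 0.3 to about 13% in model SE and 22% in empirical SD at log-SD 1.0.

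**The case against.** The planned models are valid and prespecified, and choice of covariates is a matter of discretion. Both models already adjust in part: the stratum for total hours is that endpoint's baseline exposure dichotomised, and the pain model has a related baseline count. The continuous baseline duration is averaged only over days with non-zero exposure (SAP 5.4.1.1 and 5.4.1.2). The endpoint is a 16-week sum that also depends on how many days the subject went out and on length of follow-up, so the match is imperfect. The simulations include neither dropout nor season, and both would plausibly weaken the baseline–outcome correlation. At modest settings the gain is trivial: for total hours at r = 0.3 it is worth about one subject per arm (34 × [1 - 0.981²] = 1.3 at best). The largest pain-count gains arise where the model's own SEs are least reliable.

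All of this stands, and it pulls the expected gain towards the lower end of the range. It does not remove the point. The existing terms would be kept, the closed form for total hours already credits the stratum, and the simulated downside is under 2% in empirical SD.

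**Conclusion.** The point holds as an optional improvement, not an error. That the pain count lacks a baseline pain term, and total hours a continuous baseline, is certain from the text. The size is not: it runs from nil (sparse pain, similar subjects, or weak correlation) to moderate. At the top of the assumed ranges that means about 12–13% in model SE for the pain count and about 18% for total hours at r = 0.7. These figures depend on heterogeneity, event rates and correlations that the documents do not give.

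There is no bias from the omission, because treatment is randomized and neither a linear mean difference nor a log-link rate ratio is shifted by leaving out a baseline variable. That statement covers the omission only, not early withdrawal. One secondary and one other endpoint are touched, in an exploratory trial without multiplicity adjustment (Protocol 10.2.2.1). The primary analysis is not affected.

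**What to change.** Before unblinding, in SAP 7.11.2:

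1. Add the baseline pain-event rate to the pain-count model, keeping the prodromal covariate and the stratum. Use events per baseline diary day, because baseline may cover 7 to 14 days, and prespecify the scale on which it enters.
2. Add the continuous baseline average daily symptom-free duration to the total-hours model, keeping the strata.

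Record both in SAP section 8. Although the protocol delegates model detail, it names the count covariate explicitly, and section 8 now states that nothing differs from the protocol. If unblinding has passed, report the adjusted fits as labelled sensitivity analyses.

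One question, not a criticism, because the example code is redacted and the text already promises incidence rates: please confirm that the count models use the log of observed diary days as an offset.

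The cost is two lines in 7.11.2, one entry in section 8 and one added term per model. No new data are needed and the endpoints are unchanged.

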#### **5.4.1.2 The average daily duration of sunlight exposure without prodromal symptoms**

The following is the procedure to calculate the duration of sunlight exposure without prodromal symptoms. The analysis windows are defined in the table 4.

1. Step 1 in section 5.4.1.1 will be applied.
2. The duration of sunlight exposure without prodromal symptoms in a day is calculated. It is the sum of the duration of sunlight exposure periods deducting the prodromal symptom presenting time covered in each period.
3. Step 3 to 5 in Section 5.4.1.1 will be applied.

The following endpoint is derived when applying the rule above without the step 1.

5.4.1.2.1 The average daily duration of sunlight exposure regardless of time of day without prodromal symptoms

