## 7.11 Efficacy Assessments

### 7.11.1 Primary Efficacy Analysis

The primary treatment comparisons of interest are the change from baseline in average daily time to first prodromal symptom associated with sunlight exposure between 1 hour post sunrise and 1 hour pre-sunset for the two MT-7117 doses (■, and ■) compared with placebo at Week 16 (Visit 8).

To assess the treatment effect at Week 16, change from baseline in average daily (minutes) time to first prodromal symptom associated with exposure to sunlight between 1 hour post sunrise and 1 hour pre-sunset at Weeks 2, 4, 6, 8, 10, 12, 14, and 16 will be analyzed using mixed-effect model for repeated-measures (MMRM).

The analysis model included fixed categorical terms for treatment, randomization strata (the baseline average daily sunlight exposure time without prodromal symptoms ( $\leq 30$  min or  $> 30$  min)), visit, and treatment by visit interaction together with continuous covariate terms for the corresponding baseline and the corresponding baseline by visit interaction. An unstructured correlation structure will be used to model the within-subject variance covariance errors. Should convergence of the model fail (due to the small numbers of subjects in this study), a Toeplitz correlation matrix will be used if appropriate, or else AR(1) correlation matrix will be used. The Kenward-Roger approximation will be used to estimate the denominator degrees of freedom. From the model described above, adjusted (least squares [LS]) means and standard errors will be produced by treatment and visit. Difference in adjusted means at each visit (each MT-7117 dose vs. placebo) with standard errors, 95% CIs and associated P-values will also be produced. All available data from all patients will be used in the primary analysis without any imputation. The figure of LS mean with standard error will be plotted from this MMRM.

A supportive analysis will be performed the same way for the primary endpoints using the PP population.

Non-parametric analysis will be performed in order to confirm the robustness for the above parametric model. The change from baseline in average daily time (minutes) to first prodromal symptom associated with exposure to sunlight between 1 hour post sunrise and

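### The all-hours symptom-free duration endpoint is tested by a Week 16-only ANCOVA with no missing-data rule, although the repeated-measures model planned for its in-interval counterpart would fit it unchanged

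*SAP*

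**What the plan says.** SAP 7.11.2 splits the diary-duration endpoints between two models.

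- Symptom-free duration inside the daylight interval (the first secondary endpoint) comes under this sentence: "The following continuous secondary and other efficacy endpoints will be analyzed using MMRM similar to the analyses for the primary endpoint". Its terms are treatment, stratum, visit, treatment by visit, baseline, and baseline by visit. The primary model that it refers to (SAP 7.11.1) covers Weeks 2 to 16 in two-week steps, and for that model "All available data from all patients will be used in the primary analysis without any imputation".
- The all-hours version comes under a different sentence: "The following endpoint will be analyzed using ANCOVA or ANOVA model". The endpoint is "Change from baseline in average daily duration of sunlight exposure regardless of time of day without prodromal symptoms assessed at Week 16" and the terms are given as: "The model will include fixed categorical terms for treatment, randomization strata, together with continuous covariate terms for baseline value". There is no visit term.

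SAP 5.4.1.2 links the two variables. After setting out the in-interval derivation it says "The following endpoint is derived when applying the rule above without the step 1", where step 1 is the sunrise/sunset cut. The remaining steps carry over, including the average at baseline and at each two-week time point, so the all-hours value exists at all eight post-baseline windows up to Week 16.

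Protocol 10.2.2.2 makes the same split between models. Neither document gives a reason for it.

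**The concern.** A model with one post-baseline record per subject, and no imputation rule, can use only subjects who have that record. A subject whose diary ends at Week 10 contributes five windows of all-hours data to the database and none to the test. In the in-interval MMRM, the five windows of the same subject help to estimate the Week 16 contrast.

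Two things are at stake. If subjects who have done poorly are more likely to stop the diary, the remaining subjects in an arm look better than the arm as a whole, and the Week 16 contrast is biased. Also, the two endpoints differ by design only in the daylight cut, so a reader will naturally set the results side by side. Under the current text, a difference between them could come from the cut, from the model, or from the set of subjects analysed.

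**Working it through.** **Step 1. Does any rule restore subjects without a Week 16 value?**

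| Possible rule | Where | Applies here? |
|---|---|---|
| Multiple imputation | SAP 7.11.1 | No; confined to the non-parametric analysis of the primary endpoint |
| General missing-data section | SAP 7.15.3 | No; by-time-point summaries are not imputed, and nothing is said about this ANCOVA |
| End-of-treatment row that captures early termination | SAP Table 5 | No; the table is for non-diary data |
| Diary window for Week 16 | SAP Table 4 | Days 99 to 112 only, with no early-termination row |

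The ANCOVA is therefore an observed-case analysis. That phrase is not the SAP's; it follows from a single-visit model without an imputation rule.

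**Step 2. Who is lost?** SAP 5.4.1.1 asks for only one qualifying day in the window. If a subject still keeping the diary goes out on a given day with assumed probability 0.5, independently across days, the chance of no qualifying day in 14 is 0.5^14 = 0.00006. The loss is thus almost entirely of subjects whose diary has stopped. Assuming 10% or 20% of them, the ANCOVA uses 34 × 0.9 = 30.6 or 34 × 0.8 = 27.2 per arm.

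**Step 3. Precision.** The documents state no power, SD, correlation or dropout rate, so there is no figure to reproduce, and everything below rests on assumptions. Let n = 34 per arm and let d be the fraction without Week 16, with the last observed window uniform over the first seven. Let V be the 8 × 8 correlation matrix and V_m its leading m × m block.

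- Information: I = n[(1 − d)V⁻¹ + Σ(m = 1 to 7) (d/7)V_m⁻¹], each V_m⁻¹ padded with zeros to 8 × 8.
- MMRM variance at Week 16: the last diagonal element of I⁻¹. ANCOVA variance: 1/[n(1 − d)]. The factor 2 for the arm difference cancels.

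SE ratio, MMRM to ANCOVA:

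| Correlation | d = 10% | d = 20% |
|---|---|---|
| First-order, 0.7 per window | 0.993 | 0.984 |
| First-order, 0.9 per window | 0.976 | 0.949 |
| Exchangeable, 0.7 | 0.969 | 0.936 |
| Exchangeable, 0.9 | 0.956 | 0.909 |

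The gain is about 1–9%. The calculation treats the covariance as known, so this is the favourable end.

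**Step 4. Bias.** This was simulated with two arms of 34, eight windows, and correlation 0.4 + 0.6 × 0.6^lag. The true effect rises linearly to 0.69 SD at Week 16. The dropout hazard depends on the previous observed value, with 3,000 runs per scenario. The all-visits estimate is a sequential regression, standing in for the MMRM under missing-at-random dropout.

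| Scenario | Dropout | ANCOVA mean | All-visits mean | ANCOVA bias |
|---|---|---|---|---|
| Poor responders leave, both arms | 13% | 0.665 | 0.689 | 0.690 − 0.665 = 0.025 |
| Same, higher hazard | 22% | 0.647 | 0.686 | 0.043 |
| Response-driven in placebo only | 11% | 0.619 | 0.685 | 0.071 |
| Same, higher hazard | 19% | 0.580 | 0.687 | 0.110 |

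The empirical standard errors of the two methods were almost the same (0.235–0.252 for ANCOVA, 0.235–0.256 for all visits). The benefit is mainly less bias, not precision.

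**The case against.** The case for leaving the text alone is that this is a model preference for an endpoint listed as other efficacy. The endpoint is defined at Week 16, in an exploratory trial without multiplicity control, and the SAP follows the protocol. Much of that stands, and it limits the point in four ways.

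- A reader might infer that all early leavers' data are discarded. They are not. Protocol 4.5 encourages subjects who stop treatment to complete all visits and procedures, and lets them remain on study. The diary runs to follow-up (protocol 6.7.1.1), and one qualifying day in Days 99 to 112 is enough. SAP 5.3 also provides descriptive summaries by analysis visit where appropriate, so earlier windows need not go unreported.
- A reader might infer that the all-hours endpoint is a planned check on the daylight cut. Neither document says so. Even under the same model the comparison would not be clean: without the cut, days with only early or late exposure also qualify, so the qualifying days differ.
- A reader might extend the point to the Saturday endpoint, defined as "pre-sunset on Saturday without prodromal symptoms at Week 16. The average value is calculated for Saturdays within the windows defined in section 5.4". A 14-day window holds two Saturdays, and two-day averages probably correlate less over time. With an assumed 0.3–0.5, the formula in step 3 gives a gain of only 0.1–0.6% (first-order) or 1–4% (exchangeable) at 10–20% dropout. An unstructured 8 × 8 covariance on such sparse data also raises the convergence risk that SAP 7.11.1 already anticipates. ANCOVA is a reasonable choice there.
- The larger bias figures need response-driven dropout in placebo only, and nothing in the documents points to that. With the same dropout rule in both arms the bias was 0.025–0.043 SD.

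A separate matter is that SAP 5.4.1 opens by saying that only exposure inside the daylight interval is considered and collected. An all-hours endpoint needs exposure outside it, so the two passages must be reconciled.

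What the objection does not supply is a reason to leave derived windows unused when the model for them is already specified.

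**Conclusion.** The point holds for the all-hours endpoint only. Its Week 16 ANCOVA drops subjects with no qualifying diary day in Days 99 to 112 and ignores their earlier windows, while the in-interval version of the same variable keeps them.

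The size depends on dropout that the documents do not give. At an assumed 10–20% the precision loss is small. The bias in the contrast is about 0.03–0.11 SD, which is 4–16% of the assumed 0.69 effect (0.025/0.69 to 0.110/0.69), and only if dropout follows earlier observed response. If dropout is unrelated to response there is no such bias; if it depends on unobserved values, the MMRM does not remove the bias either.

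This is a desirable improvement to an other efficacy endpoint. The documents do not support reading it as a flaw in the primary or secondary analyses.

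**What to change.** In SAP 7.11.2, move the all-hours endpoint to the MMRM list. Use the terms already given for in-interval symptom-free duration over Weeks 2 to 16 (treatment, stratum, visit, treatment by visit, baseline, baseline by visit), with the same covariance fallback as in SAP 7.11.1, and report the Week 16 contrast. This also removes the model and the missing-data handling as explanations for any difference between the two results, though the qualifying days will still differ.

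Keep ANCOVA for the in-clinic exposure test, which has one post-baseline measurement. For the Saturday endpoint the MMRM is optional; if ANCOVA stays, state how a missing Week 16 value is handled.

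Record the move in SAP section 8, because protocol 10.2.2.2 names ANCOVA or ANOVA for this endpoint. The cost is a few lines of SAP text and one more run of an existing program on a variable already derived.
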